#### Step 5: Sensitivity analyses for the impact of refusals and other sources of missing data

- We will compare patient/caregiver characteristics between those who complete the follow-up assessments and those who did not. Significant variables detected from these comparisons will be included in the ANCOVA models as covariates to control for potential bias from missing data.

**Sensitivity analyses for the impact of refusals and other sources of missing data:** Given the short time frame for collecting decision quality measures at follow-up and our pilot data, we anticipate few missing data due to caregiver refusal for the primary and main secondary outcomes. We will compare patient/caregiver characteristics between those who complete the follow-up assessments and those who did not. Significant variables detected from these comparisons will be included in the ANCOVA models as covariates to control for potential bias from missing data. Since the secondary outcome of receipt of mammogram screening will be collected from the EMR, missing data would arise only in cases of patient's death or moving out of state. We anticipate minimum missing data on the analysis of the receipt of mammogram screening.

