## **STATISTICAL POWER**

Sample size for the proposed trial is calculated using our pilot data that showed effect sizes of 0.28 on Decision Conflict Scale (DCS) score and 0.34 for self-efficacy scores. To detect effect size of 0.28 or greater on DCS scores between the two groups, we will need to have 202 patient/caregiver dyads per group to complete both baseline and follow-up with 80.2% power using two sample *t*-test at 0.05 level. Allowing 5% missing data at follow-up, we will need to enroll 213 patient/caregiver dyads per group (total 426 dyad baselines). With our planned sample size, we will have 92.6% to detect effect size of 0.34 or greater on changes in self-efficacy scores between the two groups.

The pilot showed the mean DCS were similar between the two groups, the control group had a large SD which should come down with large sample size. Table 4.

Table 4. Baseline DCS scores						
Group	N	Mean	Std Dev	Std Err	Minimum	Maximum
Control	8	26.8375	22.6769	8.0175	0	69.0000
Decision support	9	26.4444	16.4249	5.4750	0	45.0000

Change in DCS from baseline to follow-up: DA group had greater decrease in DCS than controls. The current effect size is about 0.55. Table 5.

Table 5. Change in DCS scores from baseline to follow-up, by group						
Group	N	Mean	Std Dev	Std Err	Minimum	Maximum
Control	8	5.2000	8.8073	3.1139	-6.0000	21.0000
Decision support	9	9.7778	7.8705	2.6235	0	20.0000
Diff (1-2)		-4.5778	8.3208	4.0432		

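### The only missing-data step for the T3 decisional conflict and self-efficacy outcomes is a significance-screened covariate adjustment, which is still a complete-case analysis and tests nothing about the unobserved scores

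*Combined protocol and SAP*

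**What the plan says.** Step 5 sits under a heading that calls it a sensitivity analysis for refusals and other missing data. Its content is given as a bullet and again as a paragraph. First, "We will compare patient/caregiver characteristics between those who complete the follow-up assessments and those who did not". Then, "Significant variables detected from these comparisons will be included in the ANCOVA models as covariates to control for potential bias from missing data". No significance level and no list of variables are given for the comparison.

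The same paragraph expects the problem to be minor: "we anticipate few missing data due to caregiver refusal for the primary and main secondary outcomes". It bases this on the short interval to follow-up and on pilot data. The Statistical Power section agrees with that expectation, inflating enrolment with the words "Allowing 5% missing data at follow-up" to reach 213 dyads per group.

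The documents describe no imputation, weighting, likelihood-based repeated-measures model, or delta or tipping-point analysis for DCS or self-efficacy. The primary model itself is defined in Step 2: an ANCOVA on change in DCS, adjusted for site and for baseline covariates that differ significantly between arms.

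**The concern.** A sensitivity analysis for missing data should change an assumption about the missing outcomes and show whether the conclusion survives. Adding covariates to the same ANCOVA does not do that. Caregivers without a T3 score stay out of the DCS and self-efficacy models, and the result is valid only if missingness is unrelated to outcome given whichever covariates were selected.

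The selection criterion is also incomplete. Adjusting for a variable removes bias only if it predicts both missingness and DCS, and the rule looks at missingness alone. With few non-completers, a significance test can pass over a variable that matters. With many candidates, it can admit variables that do not.

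At stake is the stated claim to control bias. If the trial is positive, the plan contains no analysis that would show whether caregivers lost before T3 could overturn the result.

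**Working it through.** **Inputs from the Statistical Power section.** Effect size 0.28 SD on DCS; 202 completing dyads per group; 80.2% power; two-sample t-test at 0.05; 5% loss; 213 per group and 426 in total enrolled; 0.34 SD and 92.6% power for self-efficacy.

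**Assumptions.** The level for the completer comparison is two-sided 0.05. True completer/non-completer differences range from 0.2 to 0.8 SD. Losses of 10%, 15% and 20% are shown as a range. None of these is a plan figure.

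**1. The plan's own figures.** With 202 per group, noncentral-t power at two-sided 0.05 is 80.2% for 0.28 SD and 92.6% for 0.34 SD. Enrolment is 202 / 0.95 = 212.6, rounded up to 213. All three reproduce.

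**2. Power of the screen.** Planned non-completers: 426 − 2 × 202 = 22, against 404 completers. For a standardised difference d, the noncentrality is d / √(1/n₁ + 1/n₂). With 22 and 404 the denominator is 0.219.

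| Loss | Non-completers v completers | d = 0.3 | d = 0.5 | d = 0.6 | d = 0.8 | d giving 50% power |
|---|---|---|---|---|---|---|
| 5% (plan) | 22 v 404 | 28% | 62% | 78% | 95% | 0.43 |
| 10% (assumed) | 43 v 383 | 46% | 87% | 96% | over 99% | 0.32 |
| 15% (assumed) | 64 v 362 | 60% | 96% | 99% | over 99% | 0.27 |

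**3. False selection.** For k irrelevant, independent variables each tested at 0.05, the chance of selecting at least one is 1 − 0.95^k. This is 40% for k = 10 and 64% for k = 20. The documents do not give k.

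**4. How far the missing scores must depart.** Suppose completers show a benefit of 0.28 SD, loss is a share m in each arm, missing control outcomes resemble control completers, and missing decision-aid outcomes are worse than decision-aid completers by δ SD. The whole-sample effect is then 0.28 − mδ. Take the standard error from completers, √(2/n) with n = 213(1 − m), and let c be the two-sided 5% t critical value times that standard error. Significance is lost at δ = (0.28 − c)/m.

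| Loss m | n per arm | c | δ at which significance is lost | Effect if δ = 0.5 |
|---|---|---|---|---|
| 5% (plan) | 202.35 | 0.195 | 1.69 | 0.255 |
| 10% (assumed) | 191.7 | 0.201 | 0.79 | 0.230 |
| 15% (assumed) | 181.05 | 0.207 | 0.49 | 0.205 |
| 20% (assumed) | 170.4 | 0.213 | 0.33 | 0.180 |

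Using 1.96 in place of the t value changes the last threshold to 0.34. At 5% loss, a 0.5 SD shift costs 0.05 × 0.5 = 0.025 SD, or 9% of the planned effect (0.025 / 0.28). At 15% it costs 0.075 SD, or 27%.

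**The case against.** The strongest reply is that the plan expects very little loss, and at that loss the matter is nearly harmless. This stands. A 0.5 SD deficit among missing decision-aid caregivers leaves 0.255 SD at 5% loss, with z = 0.255 / 0.0994 = 2.56, and overturning the result takes about 1.7 SD.

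The answer is that 5% is an expectation with thin support. Table 1 allows the primary care visit to lie up to 12 months ahead. Step 2 (Enrollment) provides for a substitute visit if none has occurred by about six months. T3 is tied to that visit. The pilot tables show 17 dyads; even if none was lost, the one-sided 95% upper limit for the loss rate is 1 − 0.05^(1/17) = 16%.

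Four stronger readings are tempting, and the documents do not support them.

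- A reader might infer that the screen will usually miss the drivers of dropout. The documents give no driver sizes. At 5% loss a 0.6 SD driver would be flagged 78% of the time, and at 15% even a 0.3 SD driver would be flagged 60% of the time. Weak screening and material bias therefore do not coincide for moderate differences.
- A reader might infer that dyads without T3 drop out of every analysis. Mammogram receipt comes from the medical record and caregiver report at T4, and from the record alone at T5. Nothing removes a dyad from the Step 3 logistic model for lacking T3.
- A reader might infer that Step 5 rewrites the primary model. Its heading allows it to be read as a supplementary refit that leaves the Step 2 ANCOVA unchanged. The text does not settle this.
- A reader might infer that multiple imputation alone would cure the problem. DCS has one follow-up, so imputing from T1 variables rests on much the same missing-at-random assumption as adjusting for them. Its use here is as the base for a delta analysis.

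**Conclusion.** The point holds for DCS and self-efficacy at T3. Step 5 delivers neither the control of bias that it claims nor a sensitivity analysis: it is a complete-case ANCOVA with covariates chosen on missingness alone, and it examines no departure from missing-at-random. That conclusion comes from the text and needs no arithmetic.

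Its size is modest. The screen is weak for small differences at the planned loss, but the possible damage at that loss is also small. The issue becomes material only if loss is well above plan, at roughly 15% or more, where a shift of half an SD or less would remove significance. These thresholds assume an observed effect of exactly 0.28 SD, equal loss by arm, missing control outcomes like observed ones, and a completer-based standard error. This is a cheap improvement rather than a threat to the trial.

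**What to change.** In Step 5:

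- Drop the significance screen as an adjustment rule. Keep the completer/non-completer comparison as description.
- Name a fixed set of T1 covariates for the ANCOVA, including baseline DCS and site, and use it whatever that comparison shows.
- Add a delta-adjusted tipping-point analysis for DCS. Impute missing T3 scores by arm from T1 variables, worsen the imputed decision-aid scores in steps until significance is lost, and report that shift alongside the observed loss in each arm.
- State whether Step 5 is supplementary to the primary ANCOVA.

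The cost is plan wording and modest SAS programming. T1 measures such as self-efficacy, knowledge, screening intention, dementia severity and health literacy are already collected, so no new data are needed. Intervals from the imputed analysis may be slightly wider. If loss does stay near 5%, the tipping-point analysis is likely to show a comfortable margin and would strengthen a positive result.

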## **STATISTICAL POWER**

Sample size for the proposed trial is calculated using our pilot data that showed effect sizes of 0.28 on Decision Conflict Scale (DCS) score and 0.34 for self-efficacy scores. To detect effect size of 0.28 or greater on DCS scores between the two groups, we will need to have 202 patient/caregiver dyads per group to complete both baseline and follow-up with 80.2% power using two sample *t*-test at 0.05 level. Allowing 5% missing data at follow-up, we will need to enroll 213 patient/caregiver dyads per group (total 426 dyad baselines). With our planned sample size, we will have 92.6% to detect effect size of 0.34 or greater on changes in self-efficacy scores between the two groups.

The pilot showed the mean DCS were similar between the two groups, the control group had a large SD which should come down with large sample size. Table 4.

Table 4. Baseline DCS scores						
Group	N	Mean	Std Dev	Std Err	Minimum	Maximum
Control	8	26.8375	22.6769	8.0175	0	69.0000
Decision support	9	26.4444	16.4249	5.4750	0	45.0000

Change in DCS from baseline to follow-up: DA group had greater decrease in DCS than controls. The current effect size is about 0.55. Table 5.

Table 5. Change in DCS scores from baseline to follow-up, by group						
Group	N	Mean	Std Dev	Std Err	Minimum	Maximum
Control	8	5.2000	8.8073	3.1139	-6.0000	21.0000
Decision support	9	9.7778	7.8705	2.6235	0	20.0000
Diff (1-2)		-4.5778	8.3208	4.0432		

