**Table 2. Sites for DECAD Recruitment\***

Site	Number of sites	# of Physician s	Women ≥70 years old with AD	Race and Ethnicity for population with AD
Eskenazi Health Aging Brain Care Program	1	5	1,383	White 42% African American 51% Other or unknown 7% Hispanic 2%
Indiana University Alzheimer Disease Center	1	NA	43	White 67.5% African American 32.5%
Indiana University Health Department of Neurology	1	3	TBD	TBD
Alzheimer's Association- Greater Indiana Chapter	5-10	NA	TBD	TBD
IU Health PC		179	2,026	White 75.6% African American 22.4%

- Caregivers will be age 18 and older and an unpaid, informal caregiver for the patient either self-identified, identified by the patient, or identified by the patient's medical team.
- See Table 1 for patient and caregiver inclusion and exclusion criteria.

*Recruitment Sites (as of 11/30/2021):*

- Aging Brain Care Program at Eskenazi Health
- Indiana University Alzheimer Disease Center (research registry)
- Indiana University Health Department of Neurology
- Indiana University Health Department of Psychiatry (Drs. [name] and [name])
- Alzheimer's Association- Greater Indiana Chapter (Support Group members)
- Indiana University Health Primary Care Practices in central Indiana
- Eskenazi Health Primary Care Practices in central Indiana
- Beth Israel Deaconess Medical Center, Boston, Massachusetts
- Parkview Health, Fort Wayne, Indiana
- CICOA Aging and In-Home Services, central Indiana
- LifeStream Services, eastern Indiana
- Thrive Alliance, southern central Indiana
- SWIRCA & More, southwest Indiana

	14 PC practices			Other or unknown 2% Hispanic 0.9%
BIDMC	7 sites	90	1600	White- 64% Black- 23% Asian- 4% Hispanic -5%
Parkview Health	TBD	TBD	TBD	TBD
CICOA Aging and In-Home Services	NA	NA	988	TBD
LifeStream Services	NA	NA	200	TBD
Thrive Alliance	NA	NA	40	TBD
SWIRCA & More	NA	NA	90	TBD
Total	34	277	6280	

\*Data as of March 2017 besides BIDMC, Parkview Health, CICOA, LifeStream, Thrive Alliance, SWIRCA & More

*Primary outcome:* Caregiver decisional conflict at post-index visit (T3)

*Secondary outcome (caregiver):* Caregiver decision-making self-efficacy at post-index visit (T3)

*Secondary outcome (patient):* Utilization of mammograms at 15 (T4) and 24 months post-index visit (T5).

Table 3. Measures							
Outcomes	Construct/Core Attributes	Outcome measure(s)	Name of Measure citation	Description	Scoring	When	Source

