- The 15 month follow-up (T4) will be in-person or via phone and include an assessment with the caregiver and a review of the patient's EMR. This interview may be audio recorded. In the event we have exhausted the attempts to reach the participant/caregiver by phone or in person, we will send a paper copy of a letter explaining the request to have them complete the survey on paper and return to the research assistant.
- The 24 month follow-up (T5) will include a review of the patient's EMR (only).
- See Table 3 and Figure 1 for a complete list of measures and timing of collection.

*Statistical Plan:*

Step 1: Overview

- For analysis, we will examine univariate distributions of continuous variables in order to detect any potential violations of assumptions to our planned parametric methods of analyses.
- We will transform variables as needed to ensure normal distribution assumptions are met.
- We will use nonparametric methods if transformations are inadequate.
- Demographic characteristics of the patients and caregivers will be compared between the two groups in order to evaluate if randomization is effectively balanced. We will include caregiver sex as a moderating biological variable and examine the influence of sex on caregivers' decisional conflict and other factors associated with the impact of our decision aid interaction on mammography screening use.
- We will use Chi-squared tests or Fisher's exact tests to compare the frequencies of categorical variables. Analysis of variance (ANOVA), or its nonparametric alternative, the Wilcoxon rank sum test, will be used to compare the distribution of continuous variables between the groups.
- We will use SAS 9.4 for all analyses (SAS Institute, Carey, NC).

Step 2: Primary Aim

- Analysis of covariance (ANCOVA) models will be used to compare mean Decisional Conflict Scale (DCS) scores between the intervention and control groups. For each caregiver, the difference in DCS scores from baseline to follow-up will be used as the dependent variable in the ANCOVA with randomization group assignment as the independent variable adjusting for the stratification variable of recruitment site and for other potential baseline covariates that are found to be significantly different between the two groups in univariate comparisons.

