- ANCOVA models will also be used to compare secondary decision quality outcome (e.g., decision-making self-efficacy) at follow-up between the intervention and control groups adjusting for site and other potential baseline covariates found to be significantly different between the two groups in univariate comparisons.

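### The self-efficacy power statement is for changes, but the plan analyses the follow-up score without fixing the baseline score as a covariate, so 92.6% need not describe that analysis

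*Combined protocol and SAP*

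**What the plan says.** **Power.** The Statistical Power section takes an effect size of "0.34 for self-efficacy scores" from the pilot, then states power of "92.6% to detect effect size of 0.34 or greater on changes in self-efficacy scores between the two groups". It gives no SD and no pilot table for self-efficacy; Tables 4 and 5 cover the Decisional Conflict Scale (DCS) only.

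**Outcome.** The outcome list after the recruitment sites gives the secondary caregiver outcome as "Caregiver decision-making self-efficacy at post-index visit (T3"). Table 3 has the self-efficacy scale collected at T1 and T3.

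**Analysis.** Statistical Plan, Step 2 (Primary Aim), uses ANCOVA to "compare secondary decision quality outcome (e.g., decision-making self-efficacy) at follow-up between the intervention and control groups". Its rule for choosing covariates in that model reads: "adjusting for site and other potential baseline covariates found to be significantly different between the two groups in univariate comparisons". For DCS, the same step says that "the difference in DCS scores from baseline to follow-up will be used as the dependent variable in the ANCOVA". It has no such sentence for self-efficacy.

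**Another route for covariates.** Step 5 compares those who complete follow-up with those who do not, and adds: "Significant variables detected from these comparisons will be included in the ANCOVA models as covariates to control for potential bias from missing data".

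**The concern.** The quantity that is powered (change) is not the quantity that is analysed (the T3 score). An effect of 0.34 SD means different things on the two scales, because the SD of a change score and the SD of a follow-up score differ unless the T1-T3 correlation takes one particular value.

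A fixed T1 covariate would largely remove the difficulty, but the plan does not provide one. T1 self-efficacy can enter only if the arms differ significantly on it, or if it distinguishes completers from non-completers. Neither is assured. Step 1 commits only to comparing demographic characteristics between the arms, so it is not even clear that T1 self-efficacy would be screened.

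Self-efficacy is named in the Primary Aim hypothesis and has its own power claim. At stake are the meaning of that claim and some precision that the collected data could supply.

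**Working it through.** **Inputs.** From Statistical Power: effect size 0.34, 202 completers per group, level 0.05, two-sample t-test. Two-sided testing is assumed because it reproduces the stated figures. The T1-T3 correlation r is not given, so it is varied from 0.2 to 0.9. Equal SDs at T1 and T3 are assumed unless stated. Site is left out.

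**1. Reproduce the plan's figures.** Noncentral t with noncentrality d × √(n/2) and 2n − 2 = 402 df:
- d = 0.34: 0.34 × √101 = 3.417, power 92.63% (stated 92.6%).
- d = 0.28: power 80.16% (stated 80.2%).
- 213 × 0.95 = 202.35, which agrees with 202 completers.

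The arithmetic is correct. The question is which analysis it describes.

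**2. Convert between scales.** With a common SD σ, the change score has SD σ√(2(1 − r)), and the T3 score given T1 has SD σ√(1 − r²).

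- If 0.34 is in change SDs: follow-up without T1 has d = 0.34√(2(1 − r)); with T1 fixed, d = 0.34√(2(1 − r))/√(1 − r²).
- If 0.34 is in follow-up SDs: follow-up without T1 has d = 0.34; with T1 fixed, d = 0.34/√(1 − r²).

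Example, change SDs, r = 0.7: d = 0.34 × √0.6 = 0.263, power 75.2%. With T1 fixed, 0.263/√0.51 = 0.369, power 95.9%.

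| r | 0.34 in change SDs: T3 without T1 | 0.34 in change SDs: T1 fixed | 0.34 in follow-up SDs: T3 without T1 | 0.34 in follow-up SDs: T1 fixed |
|---|---|---|---|---|
| 0.2 | 99.1% | 99.3% | 92.6% | 93.6% |
| 0.3 | 98.1% | 98.8% | 92.6% | 94.7% |
| 0.5 | 92.6% | 97.6% | 92.6% | 97.6% |
| 0.7 | 75.2% | 95.9% | 92.6% | 99.8% |
| 0.9 | 33.2% | 93.8% | 92.6% | over 99.9% |

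In the second column, power exceeds 92.6% when r is below 0.5 and falls below 80% when r is above about 0.66.

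**3. Why fixing T1 settles the choice of outcome.** If T3 = a + b·group + c·T1 + error, subtracting T1 from both sides gives change = a + b·group + (c − 1)·T1 + error. The group estimate, standard error and p-value are identical.

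**4. When 92.6% is a lower bound.** The residual variance with T1 fixed is the minimum over k of Var(T3 − k·T1). Setting k = 0 gives the follow-up score and k = 1 the change score, so the residual SD cannot exceed either. If 0.34 is in change or follow-up SDs, the adjusted effect is therefore at least 0.34. The lost degree of freedom is negligible: d = 0.34 on 401 df still gives 92.63%.

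**5. Where the bound fails.** If 0.34 were in baseline SDs and the T3 SD were larger by a ratio s, then with T1 fixed d = 0.34/(s√(1 − r²)):
- s = 1.2: 84.6% at r = 0.3 (d = 0.297), 90.7% at r = 0.5.
- s = 1.3: 78.5% at r = 0.3, 85.7% at r = 0.5.

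The values of s are assumptions; the documents give none for self-efficacy.

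**The case against.** The strongest reply is that the dependent variable is not really in doubt. The outcome list and Step 2 agree on T3, and the authors spell out a difference score when they want one, as they do for DCS. One word in the power section does not override the analysis section. This largely stands: the plain reading is a T3 analysis. The one qualification is that the outcome list also gives the primary outcome as "Caregiver decisional conflict at post-index visit (T3"), although Step 2 analyses it as change, so the T3 label alone is not decisive.

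Second, no loss of power is shown. If 0.34 is in follow-up SDs, 92.6% is exact for the analysis as written. This stands too. A reader might infer from the lower rows of the table that self-efficacy is underpowered. The documents do not support that: it needs both a change-SD scale and a correlation above about 0.66, and neither is given.

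Third, in a 1:1 randomised trial the T3 comparison is unbiased and keeps its type I error without T1, so the covariate is an efficiency gain. Rewording the power section to T3 and stating the scale of 0.34 would by itself cure the inconsistency. That is correct. The covariate is recommended because it costs almost nothing and makes the choice between T3 and change immaterial to the group comparison.

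**Conclusion.** The mismatch is real and minor. The power section refers to change, the analysis is most plainly of the T3 score, and T1 self-efficacy is not a fixed covariate. The 92.6% is computed correctly, but it applies to the planned analysis only if 0.34 is in follow-up SDs, or if r is about 0.5 with equal SDs. Otherwise it may be too high or too low, and the documents do not allow the direction to be settled.

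A reader might also conclude that adding T1 guarantees at least 92.6%. It does so, approximately, only if 0.34 is in change or follow-up SDs; in baseline SDs with a larger SD at T3, power can be lower.

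The sample size of 426 dyads and the primary DCS power are unaffected, and there is no bias or type I error problem. The power ranges rest on 202 completers per group, two-sided testing at 0.05 and an assumed r; the table also assumes equal SDs.

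**What to change.** - **Statistical Plan, Step 2.** State that the T3 self-efficacy score is the dependent variable, and prespecify the T1 self-efficacy score as a covariate whether or not the arms differ on it at baseline. Precision is then about equal to, or better than, either analysis without T1.
- **Statistical Power.** Name the same outcome and state which SD lies behind 0.34. If it is the change SD or the follow-up SD, 92.6% can be described as approximately a lower bound for the adjusted model. If it is any other SD, restate the power with the assumed SDs and correlation.

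The cost is one covariate already collected (one degree of freedom), one added sentence and one clarified sentence. Enrolment, visits, measures and the primary DCS analysis stay as they are.
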